8.1 Design

This is a stratified Phase II study of escalating fractions of stereotactic body *radiotherapy* (SBRT) combined with immunotherapy for previously untreated or previously treated metastatic melanoma patients. Patients will undergo a short course of high dose SBRT to a single index lesion that is suitable for SBRT. These fractions will be administered several days apart. Radiotherapy will be immediately followed by ipilimumab, at the FDA-approved dose and schedule.

Stratified Phase II study: With safety data from an identical University of Pennsylvania study, SBRT fractions of two and three fractions has been shown to be safe. At UW/SCCA the Phase II study begins with Dose Level 1. If three fractions of SBRT are found to not be safe, the dose level will be reduced to Dose level -1 for the phase II portion of that stratum.

Stratification by Site of Index Lesion						
Dose Level	Stratum 1: bone or lung			Stratum 2: liver or subcutaneous		
	Dose per fraction	Fractions	# Patients	Dose per fraction	Fractions	# Patients
-1	8 Gy	2	6	6 Gy	2	6
1	8 Gy	3	6	6 Gy	3	6

The MTD has been defined by the Phase I trial at the University of Pennsylvania as 3 fractions of SBRT. The Phase II study can commence at UW/SCCA at dose level 1 (above). Patients will be treated at the MTD defined for their index lesion site. In Phase II, patients will be stratified by disease site: Stratum 1: phase 1 bone or lung and Stratum 2: phase 1 liver or subcutaneous. Stratum-specific response rates will be calculated. Enrollment will proceed independently for the

CONFIDENTIAL

This material is the property of the study sponsor. Do not disclose or use except as authorized in writing by the study sponsor

Printed on 1/31/2017

two strata. Forty total patients will be enrolled in this phase. Thus a maximum of 40 patients will be entered at the MTD. Twenty patients will be enrolled in each stratum

8.2 Objectives:

Phase II study: The primary objectives are to determine for each stratum, immune-related clinical response rate, immune-related progression-free survival rate at 6 months (irPFS6), and overall survival rate at 12 months (OS12). The secondary objectives are to gather additional data on acute and late toxicity and immune pharmacodynamic changes.

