6.2.3 Dose fractionation and specification

The prescription dose per fraction to the PTV will be 8 Gy per fraction for a bone or lung index lesion and 6Gy per fraction for any liver or subcutaneous index lesion.

The total dose for dose level 1 (our starting dose level) will be one will be 24Gy over 3 fractions for a bone or lung index lesion and 18Gy over three fractions for any liver or subcutaneous index lesion.

If we encounter a dose limiting toxicity, we will then reduce our total dose to dose level -1. The total dose for dose level -1 will be 16Gy over 2 fractions for a bone or lung index lesion and 12Gy over two fractions for any liver or subcutaneous index lesion.

Dose rate: For the purpose of this study, dose rate utilized will be that which is commissioned by the manufacturer and the medical physics group for external beam radiotherapy delivery by the University of Washington Department of Radiation Oncology. There will be no special dose rate modifications required for this study.

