8.4 Plans for De-escalation

A DLT rate $\geq 33\%$ is considered unacceptable. Enrollment will proceed independently in the two strata. If a DLT is observed, then all subsequent patients will be treated at Dose Level -1.

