8.4.1 Escalation Design

CONFIDENTIAL

This material is the property of the study sponsor. Do not disclose or use except as authorized in writing by the study sponsor

Printed on 1/31/2017

Because of the successful outcome with 2 and 3 fractions of SBRT in the University of Pennsylvania Phase 1 trial, the initial dose level in this study will be Dose level 1 (3 fractions of SBRT).

Dose level 1. This trial will begin enrolling at dose level 1, 3 fractions of SBRT, which has been shown to be safe in the Phase 1 trial at University of Pennsylvania. However, if one DLT has been observed in any patient, then all remaining patients must be followed for 30 days after the 4th or final injection. Two or more DLTs will cause de-escalation to Dose level -1, which will be the MTD.

Dose level -1. If two or more DLTs are observed in Dose Level 1, then all subsequent patients will be treated at Dose Level -1. If DLTs are observed at dose level -1, this will cause termination of the study.

Replacement of patients: Subjects/patients who discontinue from the study for reasons unrelated to the study (e.g. personal reasons or adverse events after registration but prior to receiving study therapy) may be replaced as required for the study to meet its objectives. Patients that have received study therapy, but who withdraw for reasons unrelated to toxicity prior to the required observation period to determine absence of DLT, will not count toward dose escalation rules and may be replaced as required. The decision to remove a subject/patient and to replace dropouts will be made by the principal investigator. The replacement will receive the same treatment or treatment sequence (as appropriate) as the allocation number replaced.

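### Section 8.1 limits de-escalation to the affected stratum, but 8.4 and 8.4.1 apply it to all later patients without naming a stratum, so the scope of the DLT rule is not settled

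*Combined protocol and SAP*

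**What the plan says.** Four sections govern the move from Dose Level 1 to Dose Level -1.

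- **8.1 Design.** If three fractions are found unsafe, "the dose level will be reduced to Dose level -1 for the phase II portion of that stratum". The same section says "Patients will be treated at the MTD defined for their index lesion site", has the strata enrol independently with 20 patients each, and tabulates six patients per dose level within each stratum.
- **8.4 Plans for De-escalation.** "Enrollment will proceed independently in the two strata". The next sentence reads: "If a DLT is observed, then all subsequent patients will be treated at Dose Level -1".
- **8.4.1 Escalation Design.** "If two or more DLTs are observed in Dose Level 1, then all subsequent patients will be treated at Dose Level -1". For the lower level it adds: "If DLTs are observed at dose level -1, this will cause termination of the study".
- **6.2.3 Dose fractionation and specification.** On meeting a dose-limiting toxicity, "we will then reduce our total dose to dose level -1". The level -1 totals are then listed for each site group.

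Section 8.3 defines the MTD through 0 or 1 DLT in six patients. Section 8.4.2 tabulates the probability of escalating for true DLT rates from 10% to 90%.

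**The concern.** Section 8.1 names the stratum as the unit of de-escalation. Sections 8.4 and 8.4.1 name no unit, and the consequence in 8.4.1 at level -1 falls on the study as a whole. Suppose two DLTs occur in lung lesions and none in liver or subcutaneous lesions. The next liver patient stays at level 1 under 8.1. Under the literal words of 8.4.1 that patient moves to level -1. No sentence says which section governs.

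The primary objectives in 8.2 (response rate, irPFS6 and OS12) are set for each stratum, and 8.3 defines the response rate among patients treated at the MTD. The scope of the rule therefore decides how many fractions later patients in the unaffected stratum receive, and which dose level and denominator that stratum's primary estimates describe. At most 20 patients per stratum are exposed to the ambiguity; only those enrolled after the trigger would actually be affected.

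**Working it through.** **Step 1: scope and trigger side by side.**

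| Section | DLT trigger | Who is moved |
|---|---|---|
| 6.2.3 | one | not stated |
| 8.1 | finding that three fractions are unsafe | the affected stratum |
| 8.4 | one | all later patients, no stratum named |
| 8.4.1 | two or more | all later patients, no stratum named |

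The sections differ on scope and, separately, on trigger. The trigger conflict (one DLT in 6.2.3 and 8.4, two or more in 8.4.1) exists even within a single stratum.

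**Step 2: reproduce the plan's own table (8.4.2).** For a cohort of six with true DLT rate p, let

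S(p) = P(at most 1 DLT in 6) = (1−p)^6 + 6p(1−p)^5.

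For p = 10% to 90% this gives 0.886, 0.655, 0.420, 0.233, 0.109, 0.041, 0.011, 0.0016 and 0.00006. All nine agree with the printed 0.89, 0.66, 0.42, 0.23, 0.11, 0.04, 0.01, 0.002 and <0.001.

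Two alternatives do not fit. A one-DLT trigger (0 in 6) gives 0.531 at 10%. A count over both strata (at most 1 in 12) gives 0.659 at 10%. The table therefore describes one cohort of six with a two-DLT trigger.

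**Step 3: what the scope is worth.** Inputs from the documents: six patients per stratum at level 1 (8.1) and two or more DLTs (8.4.1). Assumption: equal true DLT rates of 10, 20 or 30% in both strata, with independent outcomes. Probability that a given stratum is reduced:

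- own count only: 1 − S(p)
- either stratum's trigger moves both: 1 − S(p)²
- DLTs pooled over both strata: P(at least 2 in 12) = 1 − (1−p)^12 − 12p(1−p)^11

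| True rate (assumed) | Own count | Either moves both | Pooled count |
|---|---|---|---|
| 10% | 1 − 0.8857 = 0.114 | 1 − 0.8857² = 0.215 | 0.341 |
| 20% | 1 − 0.6554 = 0.345 | 1 − 0.6554² = 0.571 | 0.725 |
| 30% | 1 − 0.4202 = 0.580 | 1 − 0.4202² = 0.823 | 0.915 |

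The second column exceeds the first by 0.101, 0.226 and 0.244, or about 10 to 24 percentage points.

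**Step 4: unequal rates.** Assume 33% in stratum A and 5% in stratum B, six patients each. S(0.33) = 0.3578 and S(0.05) = 0.9672. Stratum B is reduced with probability 1 − 0.9672 = 0.033 on its own count, 1 − 0.3578 × 0.9672 = 0.654 if either trigger moves both, and 0.716 if DLTs are pooled. Scope matters most when toxicity differs by site.

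**The case against.** The strongest reply is that the plan intends a within-stratum rule throughout and that 8.4 and 8.4.1 simply do not repeat the stratum. Several features support this. Section 8.1 sets the MTD by index lesion site and uses cohorts of six per stratum. Section 8.4 mentions independent strata immediately before its rule. Section 8.5 tables DLTs by stratum and dose level. The 8.4.2 figures fit six patients, not twelve.

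Much of this stands. A reader might infer that the protocol certainly gives patients in the unaffected stratum two prescriptions. The documents do not go that far: no sentence says that DLTs in one stratum lower the dose in the other. Three further inferences are also unsupported:

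- That DLTs are to be pooled over strata. No section says so, and 8.4.2 does not fit a pooled count. The own-against-pooled gap (0.227, 0.380 and 0.335 from the table) is therefore not the size of the conflict between 8.1 and 8.4.1 over who is moved.
- That the reference in 8.4.1 to a DLT in any patient extends the dose reduction. That sentence triggers follow-up of the remaining patients, not a dose change.
- That 6.2.3 reduces both sites because it lists both. It lists level 1 for both sites in the same way; only its trigger sentence, which is silent on stratum, bears on scope.

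The reply does not close the point. The independence sentence in 8.4 concerns enrolment, not DLT counting or dose assignment. Section 8.1 shows that the plan names the stratum when it means the stratum. Termination of the study in 8.4.1 leans towards a study-wide reading. The 8.4.2 table shows how DLTs were counted for that calculation, but not whether a trigger in one stratum moves the other.

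**Conclusion.** The point holds as an inconsistency in a stated safety rule. Section 8.1 confines de-escalation to the affected stratum, while 8.4 and 8.4.1 as written do not. The within-stratum reading is plausible but has to be inferred.

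Under the two-or-more trigger, six patients per stratum and equal rates of 10 to 30%, letting one stratum's trigger move both raises a given stratum's chance of reduction by about 10 to 24 points. All the rates are assumptions, since the documents report none, and the size varies with them: with 33% and 5%, the low-rate stratum goes from 0.033 to 0.654. These figures also take the two-DLT trigger as given, which 6.2.3 and 8.4 contradict.

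The 8.4.2 table is arithmetically correct for a two-DLT rule in a cohort of six, and is not itself an error.

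**What to change.** Reconcile 6.2.3, 8.1, 8.4 and 8.4.1 so that each gives the same answer to four questions:

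1. Are DLTs counted within a stratum or over both?
2. Does a trigger move later patients in that stratum only, or in both?
3. Do DLTs at level -1 end enrolment in that stratum, or the study?
4. How many DLTs form the trigger?

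Which answers are right is for the sponsor.

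Recompute 8.4.2 only if the chosen rule is something other than two DLTs in a stratum cohort of six; otherwise it can stand, with a line saying that it applies to each stratum separately. The cost is a wording amendment and at most one recalculated table, with no additional patients.

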8.3 Endpoints

Toxicity: CTCAE version 4.0 grades will be employed. Any patient who receives any amount of radiotherapy or study medication will be included in the toxicity analysis.

Dose-limiting toxicity (DLT) is defined generally as associated with the treatment, and for ipilimumab, that the event must be consistent with an immune-related effect. DLT is experienced during study treatment or within 30 days after last injection of ipilimumab, as long as the patient has not started another systemic treatment for cancer and is defined more precisely in Section 5.2.

Maximum tolerated SBRT fraction (MTD) is defined as the SBRT fraction dose level at which 0-1/6 patients experience DLT and at least 2 patients treated at the next higher dose level experience DLT (or the apparent MTD is Dose level 1).

Late toxicity is defined generally as an adverse event associated with the treatment which occurs beyond 30 days after last injection (i.e., adverse events which are observed months after treatment are most likely associated with SBRT) and is defined more precisely in Section 5.2.

Response: Immune-related clinical response will be scored on a non-index lesion using immune-related response criteria (irRC) according to irRECIST 1.1 (48). Patients who do not complete a clinical response evaluation, with the exception of those patients with rapidly progressing disease, will be scored as unevaluable. The immune-related clinical response rate is defined as the proportion of patients treated at the MTD who achieve either a complete or partial immune-related response. Unevaluable patients are included in denominator for the calculation of the objective response rate.

Immunologic outcomes include: 1) analysis of lymphocyte subsets and lymphocyte activation, 2) analysis of antigen-specific T cells and 3) tumor-specific T cells, as described in Section 7.2.2. For T cell response analyses, overall immune response is defined as >2 fold pre-treatment/post-treatment increase in any of the key T cell parameters.

8.4 Plans for De-escalation

A DLT rate $\geq 33\%$ is considered unacceptable. Enrollment will proceed independently in the two strata. If a DLT is observed, then all subsequent patients will be treated at Dose Level -1.

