8.4.2 Operating Characteristics

To assure safety in this Phase II trial, the operating characteristics of the above-defined escalation rule have been determined. The operating characteristics denote the probability of escalation to the next SBRT fraction dose level, for a *true* DLT rate at the current dose level. For a true DLT rate that is high, we desire the probability of escalation to be low. As noted in the table below, the probability of escalating beyond a certain dose level, if that dose level truly has e.g. a 40% DLT rate, is 0.23.

Operating characteristics of the escalation rule									
	True DLT rate at a particular dose level								
Probability of escalating	10%	20%	30%	40%	50%	60%	70%	80%	90%
	0.89	0.66	0.42	0.23	0.11	0.04	0.01	0.002	<0.001

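### The de-escalation trigger is one DLT in Sections 6.2.3 and 8.4 but two or more in 8.4.1, with no stated denominator, and the 8.4.2 table fits only two or more in six

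*Combined protocol and SAP*

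**What the plan says.** The trial opens at dose level 1 (three fractions). The only other level is -1 (two fractions).

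- Section 6.2.3: "If we encounter a dose limiting toxicity, we will then reduce our total dose to dose level -1".
- Section 8.4, after setting a DLT rate of 33% or more as unacceptable: "If a DLT is observed, then all subsequent patients will be treated at Dose Level -1".
- Section 8.4.1, on a single DLT: "if one DLT has been observed in any patient, then all remaining patients must be followed for 30 days", counted from the fourth or last injection. It then says "Two or more DLTs will cause de-escalation to Dose level -1, which will be the MTD", and the paragraph on level -1 repeats the two-DLT condition.
- Section 8.4.1, on level -1: "If DLTs are observed at dose level -1, this will cause termination of the study".
- Section 8.1: if three fractions prove unsafe, "the dose level will be reduced to Dose level -1 for the phase II portion of that stratum". It also says "Twenty patients will be enrolled in each stratum", and its dose table lists six patients per level in each stratum.
- Section 8.3 defines the MTD by 0-1/6 patients with a DLT, and computes the response rate among patients treated at the MTD.
- Section 8.4.2: "The operating characteristics denote the probability of escalation to the next SBRT fraction dose level". Its table runs from 0.89 at a true DLT rate of 10% to below 0.001 at 90%.

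**The concern.** Two sections reduce the dose after one DLT. A third does not reduce it until there are two. A clinician working from 6.2.3 would give the next patient two fractions; one working from 8.4.1 would give three. No text says which section governs.

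The counting window is also open. The figure of six appears in 8.1 and 8.3 but not in the trigger sentences, and nothing says whether DLTs in patients 7 to 20 of a stratum count. At level -1 the number of DLTs that stops enrolment is not given. Termination there applies to the whole study, although the strata enrol independently and de-escalate separately.

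The 8.4.2 table does not settle the matter. It describes an upward move that cannot happen in a trial that starts at its highest level.

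The trigger decides individual radiation doses. It also decides which level is the MTD, and so who enters the primary response-rate denominator.

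**Working it through.** **Inputs.** From the documents: triggers of one DLT (6.2.3, 8.4) or two (8.4.1); six per level (8.1, 8.3); 20 per stratum (8.1); 15 patients per year (3.1, 8.7); injections every three weeks (6.3), four of them, with 30 days' observation (8.4.1). Assumed: independent DLTs with a constant true rate p, counted within a stratum, and at first no observation lag.

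**Step 1: the plan's own table.** With X the number of DLTs in six patients, P(X ≤ 1) = (1−p)^6 + 6p(1−p)^5. At p = 0.10 this is 0.531 + 0.354 = 0.886. For p = 10% to 90%:

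0.886, 0.655, 0.420, 0.233, 0.109, 0.041, 0.011, 0.0016, 0.0001.

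All nine printed entries are reproduced. A search of every fixed-size rule from 2 to 40 patients found no other match. A standard 3+3 (0.906, 0.709, 0.494, …) and zero DLTs in six (0.531, 0.262, 0.118, …) do not fit. The table is therefore the probability of staying at the current level when two or more DLTs in six trigger a reduction.

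**Step 2: the other readings.** The probability of staying at level 1 is P(X ≤ 1) for a two-DLT trigger and P(X = 0) for a one-DLT trigger, over n = 6 or n = 20:

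| True DLT rate | Two in 6 (printed table) | One in 6 | Two in 20 | One in 20 |
|---|---|---|---|---|
| 2% | 0.99 | 0.89 | 0.94 | 0.67 |
| 5% | 0.97 | 0.74 | 0.74 | 0.36 |
| 10% | 0.89 | 0.53 | 0.39 | 0.12 |
| 20% | 0.66 | 0.26 | 0.07 | 0.01 |
| 30% | 0.42 | 0.12 | 0.008 | 0.0008 |

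**Step 3: patients treated at level 1.** The expected number out of 20 is the sum over k = 1 to 20 of P(DLTs among the first min(k−1, c) patients are below the trigger), with c = 6 or 20. In the column order above:

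- at 10%: 18.2, 12.1, 14.9, 8.8
- at 5%: 19.5, 15.6, 18.1, 12.8
- at 2%: 19.9, 18.1, 19.6, 16.6

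**Step 4: observation lag.** Four injections span 3 × 21 = 63 days. Adding 30 days of observation and an assumed 7 to 14 days for SBRT gives 100 to 107 days. With accrual split evenly, 15/2 = 7.5 patients per year per stratum, so about two patients enter each stratum in that time. If only DLTs in the first 17 to 19 patients can change a dose, the 10% figures over 20 become 0.42 to 0.48 (two-DLT) and 0.14 to 0.17 (one-DLT). The ordering is unchanged.

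**Step 5: stopping at level -1.** Take an assumed 5% true rate, given that de-escalation has happened. With the six patients listed in 8.1, the chance of termination is 1 − 0.95^6 = 26% if one DLT is enough and 3% if two are needed. With 14 patients (20 − 6, as when the first six were treated at level 1), it is 51% and 15%.

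**The case against.** The best reply is that the plan's intent can be inferred. The 0-1/6 definition in 8.3, the six-per-level column in 8.1, the Study Summary's statement that cohorts had six patients, the 33% criterion (2/6) and the 8.4.2 table all point to two or more in six. On that view 6.2.3 and 8.4 are loose shorthand and the escalation wording is left over. Much of this stands: two in six is the most coherent reading, and the table label alone would be editorial. But the one-DLT rule appears in two sections, each naming the dose change, and no inference about six settles what a DLT in patient 12 does.

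It can also be said that the four readings are a reviewer's construction. No section writes one in six, running the count to 20 is an assumption, and pooling across strata is left out. That is fair. The figures show how far the ambiguity reaches, not what the plan intends.

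Third, DLT rates may be low. Section 5.2 requires a probable or definite relation to radiation, and the plan reports that three fractions were safe elsewhere. The documents give no rate. At 2% the readings differ much less, from 0.67 to 0.99. At 5% they still run from 0.36 to 0.97.

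Finally, Sections 3.1 and 8.7 allow pauses in accrual, which would shorten the lag in Step 4. That calculation is secondary and the conclusion does not depend on it.

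**Conclusion.** The concern holds. The conflict between one DLT and two is explicit in the current text and nothing resolves it. The denominator is implied as six but never attached to the trigger, and the stopping rule at level -1 lacks a count, a denominator and a consistent scope. The printed operating characteristics are correct for one rule, two or more in six, that the trigger text does not state. They do not describe the one-DLT rule in 6.2.3 and 8.4.

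At a 10% true rate, the chance of staying at level 1 ranges from 0.89 down to 0.12, and the expected number treated there from 18.2 down to 8.8 of 20. These sizes rest on independent DLTs counted by stratum and on assumed DLT rates, and they shrink if DLTs are rare. Every alternative leaves level 1 earlier than the table implies. The harm is therefore inconsistent conduct, early abandonment of a tolerable dose and an uncertain MTD population, not concealed toxicity. Because the rule sets individual patients' doses, it must be corrected.

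**What to change.** Write the same trigger in 6.2.3, 8.4 and 8.4.1. The version that agrees with the 33% criterion, the MTD definition and the existing table is two or more DLTs among the first six patients in a stratum. The clinical choice of trigger stays with the investigators.

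Also state:

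- what rule applies to DLTs in patients 7 to 20;
- how patients already on level 1 are handled when the trigger fires;
- the DLT count and denominator that stop level -1, and whether that closes the stratum or the whole study.

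Relabel the 8.4.2 table as the probability of remaining at level 1, or recompute it to show the probabilities of de-escalating and of terminating under the final rule, including patients 7 to 20.

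The cost is protocol wording and one table. No patients or procedures are added.
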